9.3.4.3 COVID-19 Sensitivity Analysis

A sensitivity analysis will be undertaken performing the primary endpoint analysis in all participants, but excluding events deemed to be COVID-19 related by the CEC. This analysis will use the same time from randomization +1 in the primary analysis.

9.4 Subgroup Analyses

Subgroup analyses will be performed on the primary endpoint to assess whether the intervention effect is consistent across all participants, or whether it varies according to specific participant characteristics. In particular, these analyses will focus on whether the relative intervention effect compared to usual care differs according to the baseline variables listed in the section 4.2.1.

The effect of the treatment strategy may also be examined in other (post hoc) subgroups of clinical interest based on initial analyses. These subgroups will be described in the CSR.

9.5 Alternative Treatment Assignment Analyses

Five additional analysis will be performed on the primary endpoint to assess whether the intervention effect size estimates vary to a clinically relevant extent according to adherence to the protocol and/or management actually received. The five are as follows:

- Including only Intention-To-Treat participants from the low risk strata
- Including only Intention-To-Treat participants from the elevated risk or known atherosclerosis strata
- Including only Per-Protocol participants
- Including only Per-Protocol participants from the low risk strata
- Including only Per-Protocol participants from the elevated risk or known atherosclerosis strata

10. Planned Table of Contents for Analysis Tables and Figures

The following tables and graphs are required for the Clinical Study Report and trial outcomes analyses. All tables are listed here for completeness.

Standard conventions will be used in table display such that the following data columns will be included: “All Usual Care” including total and additional columns of usual care split into “Low Risk” and “Elevated Risk”; “All precision care” columns will include total and additional as assigned columns indicated as “No Testing” and “CTA.”

Table/Graph Number	Table/Graph Title
Table 1.1	Participant Disposition All Randomized Participants
Table 2.1	Participant Demographics All Randomized Participants
Table 2.2	Cardiovascular Disease History; atherosclerosis history and Cardiovascular Risk Factors and risk scores All Randomized Participants
Table 2.3	Presenting Symptoms All Randomized Participants
Table 2.4	Medical History/Past Surgeries/ All Randomized Participants
Table 2.5	Physical Examination at Baseline All Randomized Participants
Table 2.6	Rest ECG Findings at Baseline All Randomized Participants
Table 2.7	Laboratory Testing at Baseline All Randomized Participants
Table 2.8	Concomitant Cardiovascular Medications at Baseline All Randomized Participants
Table 2.9	Quality Of Life at Baseline All Randomized Participants
Table 2.10	Prevention Motivation at Baseline All Randomized Participants
Table 3.1	Summary of Follow-up Visits All Randomized Participants

Table/Graph Number	Table/Graph Title
Table 3.4	Flow Chart Diagnostic Testing, Escalation (precision arm only) All Randomized Participants
Table 3.4.1	Flow Chart 1st Diagnostic Testing Randomized Tests All Randomized Participants
Table 3.5.1	1st Diagnostic Test Findings overall and by test type Site interpretation Positive/Negative Results All Randomized Participants
Table 3.5.3	2nd Diagnostic Test Findings by test type Site interpretation Positive/Negative Results All Randomized Participants
Table 3.5.4	Diagnostic Test Findings - Site interpretation Four Tier Results All Randomized Participants
Table 4.1	Primary Efficacy Analysis Endpoint Collection and Summary All Randomized Participants
Figure 4.1.1	Primary Efficacy Analysis Kaplan-Meier Plot of Primary Endpoint All Randomized Participants
Figure 4.1.2	Primary Efficacy Analysis Kaplan-Meier Plot of Primary Endpoint Component All Cause Death All Randomized Participants
Figure 4.1.3	Primary Efficacy Analysis Cumulative Incidence Plot of Primary Endpoint Component 1st Non-fatal MI All Randomized Participants
Figure 4.1.4	Primary Efficacy Analysis Cumulative Incidence Plot of Primary Endpoint Component 1st Invasive cardiac catheterization without obstructive CAD All Randomized Participants
Table 4.2	Primary Endpoint Adjusted Cox Model All Randomized Participants
Table 4.2.1	Sub-group Analyses Primary Endpoint All Randomized Participants
Figure 4.2.1.1	Sub-group Forrest Plot Primary Endpoint All Randomized Participants
Figure 4.2.2.1	Sub-group Forrest Plot Primary Endpoint All Randomized Low Risk Participants
Figure 4.2.2.2	Sub-group Forrest Plot Primary Endpoint All Randomized Elevated Risk + Athero Participants
Figure 4.2.2.3	Sub-group Forrest Plot Primary Endpoint Per Protocol Participants
Figure 4.2.2.4	Sub-group Forrest Plot Primary Endpoint Per Protocol Low Risk Participants
Figure 4.2.2.5	Sub-group Forrest Plot Primary Endpoint Per Protocol Elevated Risk + Athero Participants
Table 4.2.4.1	Primary Endpoint Cox Model Results All Randomized Low Risk Participants
Table 4.2.4.2	Primary Endpoint Cox Model Results All Randomized Elevated Risk + Athero Participants

Table/Graph Number	Table/Graph Title
Table 4.2.4.3	Primary Endpoint Cox Model Results Per Protocol Participants
Table 4.2.4.4	Primary Endpoint Cox Model Results Per Protocol Low Risk Participants
Table 4.2.4.5	Primary Endpoint Cox Model Results Per Protocol Elevated Risk + Athero Participants
Table 4.3	Primary Endpoint using unmatched Win-Ratio All Randomized Participants
Table 4.5	Cardiovascular Death Summary
Figure 4.5.1	Cumulative Incidence Plot of Cardiovascular Death All Randomized Participants
Figure 4.5.2	Cumulative Incidence Plot of Non-Cardiovascular Death All Randomized Participants
Table 4.7	Hospitalization Summary
Figure 4.7.1	Cumulative Incidence Plot of Time to 1st CV Hospitalization (CEC) All Randomized Participants
Figure 4.7.2	Cumulative Incidence Plot of Time to 1st Unstable Angina Hospitalization All Randomized Participants
Figure 4.7.3	Cumulative Incidence Plot of Time to 1st Non-CV Hospitalization All Randomized Participants
Table 4.8	Preventive Medication Summary
Table 4.9	Cumulative Radiation Exposure Summary
Figure 4.9.1	Waterfall plot of Cumulate Radiation Exposure
Figure 4.9.2	Waterfall plot of Cumulate Radiation Exposure All Randomized Participants, Excluding Low Risk Participant
Table 4.10	Revascularization Summary
Figure 4.10.1	Cumulative Incidence Plot of 1st Revascularization All Randomized Participants
Table 4.11.1.1	Prevention Motivation Descriptive Summary Day 45 Descriptive Summary
Table 4.11.1.2	Prevention Motivation Descriptive Summary 12 Month Descriptive Summary
Table 4.11.2	Prevention Motivation Testing Results Response at 45 Days All Randomized, As Tested Participants
Table 4.11.4	Prevention Motivation Method of Communication at 45 Days All Randomized, As Tested Participants
Table 4.11.5	Prevention Motivation Association of Method of Communication and Change in Motivation at 45 Days All Randomized Participants, Received Test Results
Table 4.11.6.1	Prevention Motivation Association of Medication Use and Change in Motivation at 45 Days All Randomized Participants
Table 4.11.6.2	Prevention Motivation Association of Medication Use and Change in Motivation at 12 Months All Randomized Participants
Figure 4.12.1.1	Mean observed and predicted mean Prognostic Value of Risk Score PRECISE primary endpoint all three components All Randomized Participants
Table 4.12.1.2	Mean observed and predicted mean Prognostic Value of Risk Score for PRECISE primary endpoint all three components All Randomized Participants
Figure 4.12.2.1	Mean observed and predicted mean

Table/Graph Number	Table/Graph Title
	Prognostic Value of Risk Score PRECISE primary endpoint two components: Death/MI only All Randomized Participants
Table 4.12.2.2	Mean observed and predicted mean Prognostic Value of Risk Score for PRECISE primary endpoint two components: Death/MI only All Randomized Participants
Figure 4.12.3.1	Mean observed and predicted mean Prognostic Value of Risk Score for Lowest risk: No CAD + No Event All Randomized Participants, Only Precision Care Arm Receiving CTA
Table 4.12.3.2	Mean observed and predicted mean Prognostic Value of Risk Score for Lowest risk: No CAD + No Event All Randomized Participants, Only Precision Care Arm Receiving CTA
Figure 4.12.4.1	Mean observed and predicted mean Prognostic Value of Risk Score for Significant or Severe CAD All Randomized Participants, Only Precision Care Arm Receiving CTA
Table 4.12.4.2	Mean observed and predicted mean Prognostic Value of Risk Score for Significant or Severe CAD All Randomized Participants, Only Precision Care Arm Receiving CTA
Table 4.13.1	Comparisons of outcomes in low PRMS and elevated risk Adjudicated Endpoint Collection and Summary All Randomized Participants, Low PRMS Only
Figure 4.13.1.1	Kaplan-Meier Plot of Primary Endpoint All Randomized Participants, Low PRMS Only
Figure 4.13.1.2	Kaplan-Meier Plot of Primary Endpoint Component All Cause Death All Randomized Participants, Low PRMS Only
Figure 4.13.1.3	Cumulative incidence Plot of Primary Endpoint Component 1st Non-fatal MI All Randomized Participants, Low PRMS Only
Figure 4.13.1.4	Cumulative incidence Plot of Primary Endpoint Component 1st Invasive cardiac catheterization without obstructive CAD All Randomized Participants, Low PRMS Only
Table 4.13.2	Comparisons of outcomes in low PRMS and elevated risk Adjudicated Endpoint Collection and Summary All Randomized Participants, Elevated PRMS+athero Only
Figure 4.13.2.1	Kaplan-Meier Plot of Primary Endpoint All Randomized Participants, Elevated PRMS+athero Only
Figure 4.13.2.2	Kaplan-Meier Plot of Primary Endpoint Component All Cause Death All Randomized Participants, Elevated PRMS+athero Only
Figure 4.13.2.3	Kaplan-Meier Plot of Primary Endpoint Component 1st Non-fatal MI All Randomized Participants, Elevated PRMS+athero Only
Figure 4.13.2.4	Kaplan-Meier Plot of Primary Endpoint Component 1st Invasive cardiac catheterization without obstructive CAD All Randomized Participants, Elevated PRMS+athero Only
Table 4.15.1	COVID-19 Sensitivity Analysis of Primary Endpoint Endpoint Collection and Summary All Randomized Participants

11. Changes from the Protocol

The current version of the protocol is v1.5, dated 15- OCT-2019. Under section VIII.B., the time to event is defined as the date of the first event minus the date of randomization, and we are adding 1 to this value.

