5.2 Per-Protocol

Clinicians have the option to pursue alternative diagnostic pathways if they deem it to be in the best interest of the participant, with the reason for study protocol deviation documented. The per-protocol treatment assignment is met when randomized participants received their initial evaluation as randomized. Trial participants who crossed over to the other randomized arm and those who were assigned to testing in either arm and who received no testing are excluded from analysis using this definition of treatment assignment. In addition, participants in whom all inclusion criteria were not present or in whom one or more exclusion criterion were present will be excluded from the per protocol population.

Per Protocol Definition

- Meets all inclusion/exclusion criteria
- Precision Care Participants
 - Low Risk
 - No testing OR
 - First test is a CTA
 - Elevated Risk
 - First test is a CTA
- Usual Care
 - No CTA performed < 45 days post randomization
 - Low Risk
 - First test is a Usual Care Test
 - Coronary angiography without noninvasive testing
 - Stress cardiac MRI
 - Stress echocardiography (exercise or pharmacologic stress)
 - Stress nuclear perfusion (MPI or PET; exercise or pharmacologic stress)
 - Treadmill ECG without imaging
 - Elevated Risk
 - First test is a Usual Care Test
 - Coronary angiography without noninvasive testing
 - Stress cardiac MRI
 - Stress echocardiography (exercise or pharmacologic stress)
 - Stress nuclear perfusion (MPI or PET; exercise or pharmacologic stress)
 - Treadmill ECG without imaging

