9.2 Primary Efficacy Analysis

The primary endpoint of this study is estimated as time to first occurrence of any of its three following components:

- All-cause death
- Non-fatal MI
- Invasive cardiac catheterization without obstructive CAD

Each death will be adjudicated for cause and date by the CEC. Potential MI cases will be adjudicated for MI yes/no, fatal/non-fatal, MI type, and date of MI by the CEC. Cath without obstructive CAD is the absence of obstructive CAD, defined as diameter stenosis $\geq 50\%$ in a vessel ≥ 2 mm both assessed by QCA (or site read if QCA is not available), $FFR \leq 0.80$, or $iFR \leq 0.89$. The catheterization component of the primary endpoint will be determined according to the algorithm diagrammed below:

To derive the catheterization component of the primary endpoint, site, core lab and DCRI entered clinical data present in the clinical EDC will be extracted and processed through a HeartFlow Cath Algorithm to be classified as Obstructive CAD, No Obstructive CAD, Indeterminate, or Incomplete data. Each ICA classified as either Obstructive CAD, No Obstructive CAD, or Indeterminate will undergo individual Medical Monitor review. For ICAs receiving a final classification as confirmed Obstructive CAD or No Obstructive CAD, the results are considered final. For ICAs confirmed by the Medical Monitor as Indeterminate or ambiguous, CEC adjudication will make the final determination. Incomplete ICAs will be reprocessed through the Cath Algorithm once data are complete and query free.

The time from randomization to the first event among the components of the primary endpoint will be measured (in days) for those who experienced an event and calculated as the date of the first event minus the date of randomization + 1. For participants who do not experience any of the primary component events or who withdraw consent or drop out of the study before experiencing an event, time from randomization to the date of last contact + 1 will be used in the analysis, and those participants will be considered as censored observations in the time-to-event analysis. The 12-month analysis will be censored at 395 days (365 days + 30 day visit window) such that only events on or before this time will be counted in the analysis and event free participants with follow-up greater than 395 will be set to 395.

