The primary and major secondary endpoint comparisons between the randomized groups in this study will be performed according to the principle of intention-to-treat; that is, participants will be analyzed according to the treatment (evaluation) arm to which they were randomized, regardless of subsequent crossover or post-randomization strategy.

The log-rank a non-parametric test will be the primary statistical methodology to test for outcome differences between precision care arm and usual care arm with respect to the primary composite endpoint. The Cox proportional hazards model will be used to estimate the average treatment effect size using the hazard ratio (HR) and 95% confidence interval (CI) with treatment assignment as the only covariate in the model. The proportionality assumption (constant hazard over time) in the Cox model will be assessed using the cumulative sums of martingale residuals and the Kolmogorov-type Supremum test. Although log-rank statistic (primary method) is robust under non-proportional hazards it's not optimal due to loss of some statistical power. Thus, if the proportional hazards assumption is violated a two-stage procedure will be implemented (Qiu and Sheng 2008). Due to interim analysis conducted by the DSMB, the final analysis type I error rate (α) will be adjusted as $0.05 - \alpha$ spent at any interim analyses. Cumulative event rates will be calculated according to the method of Kaplan-Meier for each randomized arm as a function of time (in days) from randomization to the time of event or censoring + 1, and the estimated event probabilities will be displayed graphically.

As a supportive analysis, adjusted HRs and 95% CIs will be estimated using the Cox proportional hazards model by including pre-specified baseline risk factors as covariates in the model. These covariates will include: age, sex, CAD equivalent (diabetes, history of peripheral artery disease, or cerebrovascular), and intended first test strata: invasive/non-invasive.

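### The per-protocol hazard ratios in SAP 9.5 rest on post-randomization selection with no correction planned, and in the low-risk strata that selection differs between arms

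*SAP*

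**What the plan says.** SAP 5.2 defines the per-protocol set by eligibility and by the evaluation actually received. Participants who crossed over are excluded, and "those who were assigned to testing in either arm and who received no testing are excluded from analysis". The arm-specific rules for the low-risk strata then differ:

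- **Precision care, low risk:** adherent with no test at all, or with a CTA as first test.
- **Usual care, low risk:** adherent only if "First test is a Usual Care Test" and no CTA was done in the first 45 days. The list of qualifying tests includes "Coronary angiography without noninvasive testing".

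In the elevated-risk strata both arms must have had their assigned type of test.

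SAP 9.5 applies the primary endpoint to the whole per-protocol set and to its low-risk and elevated-risk parts, and lists the two matching intention-to-treat subsets alongside. The aim given there is "to assess whether the intervention effect size estimates vary to a clinically relevant extent according to adherence to the protocol". It names no model, covariates or weights. The Cox model in SAP 9.2 is fitted "with treatment assignment as the only covariate in the model". The covariate-adjusted model there is a separate supportive analysis, and in SAP section 10 only Table 4.2, for all randomized participants, is titled as adjusted. The per-protocol tables (4.2.4.3 to 4.2.4.5) are not; Table 4.2.4.4, for example, is "Primary Endpoint Cox Model Results Per Protocol Low Risk Participants".

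**The concern.** The stated purpose is to learn whether the effect depends on adherence. Deleting people for what happened after randomization mixes any such effect with differences between those deleted and those kept.

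In the low-risk strata the same behaviour, having no test, leads to retention in one arm and deletion in the other. The usual-care group becomes a subset selected on testing, while the precision group still contains its untested members. The primary endpoint includes "Invasive cardiac catheterization without obstructive CAD", so who goes on to testing plausibly relates to who has events.

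Safely deferring testing in low-risk patients is described as a core secondary objective (Protocol III.A). A low-risk per-protocol hazard ratio more favourable than the intention-to-treat one could be taken as support for deferral when part of the difference is selection.

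**Working it through.** The plan states no figure for the per-protocol analyses, so there is none to reproduce. The check asks how far selection alone could move the low-risk estimate from 1 when the two strategies truly do not differ.

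**Inputs from the documents**
- 1050 participants per arm; about 20% assigned to no planned testing; overall 10% not receiving their randomized evaluation; design rates of 8% and 5% (SAP 7).
- Low-risk participants per arm: 0.20 x 1050 = 210.
- Annual clinical event rate about 1-2% (Protocol III.A); CV death/MI below 1% per year in the low-risk category (Protocol IX.B).
- Day-45 visit window of 14 days either side (Protocol V.D), closing on day 45 + 14 = 59.

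**Assumptions**
- Untested share u of low-risk usual care: 10% or 20%. The SAP's 10% covers all non-receipt in both arms and is only a guide.
- A baseline score S with a standard normal distribution. The odds ratio per SD is 0.33 to 0.50 for being untested and 1.5 to 3 for having an event if tested.
- Mean event risk 5% under full adherence in both arms.

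**Formula.** Let p(S) be event risk if tested. Precision care keeps everyone, so its mean risk is E[p(S)]. Usual care keeps only the tested, so its mean is E[p(S) | tested]. The null per-protocol relative risk is

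RR = E[p(S)] / E[p(S) | tested].

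Both logistic intercepts are set so that the averages are u and 5%, and the expectations are taken by numerical integration.

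| u | OR untested, OR event | Risk if tested: those tested | Risk if tested: those untested | RR |
|---|---|---|---|---|
| 10% | 0.50, 1.5 | 5.12% | 3.96% | 0.98 |
| 10% | 0.33, 3 | 5.34% | 1.92% | 0.94 |
| 20% | 0.50, 1.5 | 5.23% | 4.08% | 0.96 |
| 20% | 0.33, 3 | 5.71% | 2.17% | 0.88 |

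Example: 5.00 / 5.34 = 0.94. Using 8% instead of 5% gives the same ranges to two decimals. If S were unrelated to either testing or events, RR would be 1. If those who skip testing were the higher-risk ones, RR would exceed 1.

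**Scale.** With 8% in both arms the low-risk strata yield 2 x 210 x 0.08 = 33.6 events, so SE(log HR) is about 2/sqrt(33.6) = 0.35. With 5% they yield 21 events and the SE is 2/sqrt(21) = 0.44. Since ln 0.94 = -0.06 and ln 0.88 = -0.13, the largest shift is about 0.14-0.18 SE at 10% untested and 0.30-0.37 SE at 20%.

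**Deaths before the test.** A usual-care participant who dies untested is also deleted, with the event; the low-risk precision counterpart is kept. This acts against precision care. If testing takes 3 to 6 weeks (taken as 21 to 45 days), death-or-MI events in that period number 210 x (0.01 to 0.02) x (21 to 45)/365 = 0.12 to 0.52 per low-risk arm. At the 1% ceiling quoted for this category the figure at day 45 is 0.26. Deaths are only part of these.

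**The case against.** The strongest reply has four parts.

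1. **The asymmetry belongs to the strategies.** No test is the assigned low-risk precision strategy, whereas usual care requires an initial test (SAP 2). Keeping one group and dropping the other is faithful to the two definitions. This stands: the rule is not an error. What it does not do is make the resulting groups comparable.

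2. **The direction is not established.** A reader might infer that the tilt toward precision care follows from the definitions, because an untested usual-care participant cannot have had a catheterization. The documents do not support that. A per-protocol analysis targets the rate under adherence, so bias depends on what the untested would have experienced if tested. Suppose the overall rate is 8%, a tenth are untested, and the untested have 0-1% events. Deletion then raises usual care to (8 - 0.1 x 0)/0.9 = 8.9%, or (8 - 0.1 x 1)/0.9 = 8.8%, and a null hazard ratio becomes 0.90-0.91. That is a departure from the intention-to-treat rate. If the untested were a random tenth, 8.8-8.9% would be the correct full-adherence rate and there would be no bias. No passage says who skips testing.

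3. **The inputs are assumed.** The odds ratios and the 20% are not in the documents, and the 10% is not specific to untested low-risk usual-care participants. This stands, so the ranges are illustrations.

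4. **The analyses are supportive.** Primary inference is by intention to treat, the matching intention-to-treat subsets sit beside the per-protocol ones in 9.5, and testing received is tabulated (Tables 3.4 and 3.4.1). No decision rule uses the per-protocol results. Also, that the model is unadjusted is inferred from 9.2 and the table titles. All of this limits the consequence; none of it supplies a correction for the selection.

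**Conclusion.** The point holds as a limited one. As planned, the per-protocol hazard ratios cannot be read as adherence effects, because the set is chosen on post-randomization testing with no correction, and in the low-risk strata the choice differs by arm. A shift toward precision care arises if those who skip testing are at lower risk when tested. On the assumed inputs the null relative risk is 0.94-0.98 at 10% untested and 0.88-0.96 at 20%, below 0.4 SE throughout. Deleted pre-test deaths act the other way, with well under one expected event in a low-risk arm.

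The elevated-risk strata drop untested participants from both arms, so this asymmetry does not arise there, although ordinary post-randomization selection does. The whole per-protocol set carries the asymmetry in diluted form, since low-risk participants are about a fifth of it. A reader might also infer that the trial's main conclusion is at risk; it is not, because the primary analysis and the two intention-to-treat subsets do not use the SAP 5.2 per-protocol definition.

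**What to change.** In SAP 9.5:

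- **Add weighted estimates.** Fit the Cox model with each per-protocol participant weighted by the inverse of the modelled probability of meeting 5.2, with robust standard errors. Report these beside the unweighted results in Tables 4.2.4.3 to 4.2.4.5.
- **Keep the weight model small.** Fit it by arm on a few baseline variables already collected, such as intended first test, PROMISE score and SAQ angina frequency. Pool the risk strata within an arm where their adherence rules match, as they do in usual care. At 10% non-adherence, low-risk usual care alone would supply only about 0.10 x 210 = 21 non-adherers; pooled usual care would supply about 0.10 x 1050 = 105.
- **Handle pre-test deaths explicitly.** Count a participant who dies before the assigned test and before the day-45 visit window closes (day 59) as adherent to that point, with the event included and a weight of 1. Such participants are retained with certainty, so up-weighting them by about 1/0.9 = 1.11 would overcount those deaths by about 11%.
- **State the interpretation.** Say that a difference between the per-protocol and intention-to-treat estimates is not by itself evidence of an adherence effect.

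The cost is SAP wording and modest programming, with no change to data collection, sample size or the primary analysis. The downside is wider intervals, and the weights correct only for measured baseline differences.
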